3.1 Inclusion Criteria

- 3.1.1 Patients must have a histologically documented (either primary or metastatic site) diagnosis of advanced solid tumor cancer (stage IV or unresectable) or aggressive lymphoma (diffuse large B cell lymphoma, mantle cell lymphoma, T cell lymphoma, and NK cell lymphoma).
NOTE: *The following histologies will be excluded given known response to PD-1/PD-L1 inhibitor monotherapy: non-small cell lung cancer, squamous cell carcinoma of head and neck, melanoma, renal cell carcinoma, bladder cancer, Hodgkin's lymphoma, Merkel cell carcinoma, and MSI-H colorectal cancer.*
NOTE: *Patients with deleterious BRCA 1/2 mutated ovarian cancer will be excluded given its presumed efficacy with veliparib monotherapy.*
- 3.1.2 All patients must have received, and be relapsed/refractory to at least one line of systemic therapy.
NOTE: *This does not include surgery or radiation alone. Patients may have received any number of systemic therapies*
NOTE: *For patients with aggressive lymphoma, there should be no other standard therapies that would confer survival benefit.*
- 3.1.3 All patients with relapsed/refractory lymphoma must have received or be ineligible for autologous stem cell transplant or be ineligible for allogeneic stem cell transplant.
NOTE: *Patients must not have had a prior allogeneic stem cell transplant.*
- 3.1.4 Patients must have measurable disease as per appropriate guidelines:

- Solid tumors: by RECIST v1.1
- Lymphoma: Patient has at least one measurable nodal lesion (≥2 cm) according to Lugano classification. If the patient has no measurable nodal lesions ≥2 cm in the long axis at screening, then the patient must have at least one measurable extra-nodal lesion.

3.1.5 Patients must have the ability to understand and the willingness to sign a written consent prior to registration in the study.

3.1.6 For expansion cohort patients, the profiling must reveal at least one mutation in the following selected DNA repair genes involved in cell cycle arrest signal transduction, BRCA1 pathway, Fanconi's proteins pathway, and RAD51 pathway: [ATR, ATM, CHEK1, CHEK2, BRCA1, BRIP1, BAP1, BARD1, FANCD2, FANCE, FANCC, RAD50, FANCA, RAD51, BRCA2, PALB2, CDK12 (ENSG00000167258, also known as CRK7, CRKR, CRKRS), POLE, POLD1, BRAC2, PRKDC, ERCC2, POLQ, MRE11A, NBN (MBS1)], or at least one gene amplification in FANCD2, FANCE, FANCC, FANCA, C11orf30 (EMSY).

Please note: This eligibility criteria is also applicable for patients enrolled for the preliminary expansion cohort to conduct preliminary efficacy analysis.

NOTE: Tissue or blood cell free DNA are allowed for genomic profiling of tumor. Profiling should have been performed at a CLIA certified lab ≤1 year prior to registration.

NOTE: Patients in the dose escalation phase are not required to have such mutations. Although genomic profiling is not required for dose escalation patients, it is encouraged in these patients prior to or after study registration if feasible.

3.1.7 Patients must be age ≥ 18 years; both male and females are eligible.

3.1.8 Patients must exhibit an ECOG performance status of ≤2.

3.1.9 Patients must have adequate organ and bone marrow function ≤ 14 days prior to registration, as defined below (Note: Blood transfusion or growth factors is not permitted within 14 days of registration):

absolute neutrophil count	≥ 1.5 x 10 ⁹ /L
hemoglobin	≥ 9 g/dL
platelets	≥ 100 x 10(9)/L
Total bilirubin	≤ 1.5 x ULN
Alanine amino transferase and aspartate aminotransferase	≤ 5 x ULN
Calculated creatinine clearance according to the Cockcroft and Gault equation	≥ 50 mL/min

3.1.10 Females of child-bearing potential (FOCBP) and men who are sexually active with FOCBP must agree to follow instructions for method(s) of contraception for the duration of treatment and the designated post-treatment period (5 months for females and 7 months for males; see Appendix A for details on appropriate contraception methods)

NOTE: A FOCBP is any woman (regardless of sexual orientation, having undergone a tubal ligation, or remaining celibate by choice) who meets the following criteria:

- Has not undergone a hysterectomy or bilateral oophorectomy
- Has had menses at any time in the preceding 12 consecutive months (and therefore has not been naturally postmenopausal for > 12 months)

3.1.11 FOCBP must have a negative pregnancy test ≤ 7 days prior to registration.

3.1.12 Patients must be able to swallow oral medication.

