3.0 PATIENT ELIGIBILITY

The target population for this study is patients with advanced solid tumors and lymphoma with and without mutations in selected DNA repair genes, where the expansion cohort will be reserved for patients with DNA repair gene mutations as listed in 3.1.6. This will be a single-center trial conducted at Northwestern University.

The initial study design was to accrue a total of up to 50 patients (for 48 evaluable) to the study in two phases: dose escalation and dose expansion. The original design anticipated a total of 6-18 patients with advanced solid tumors or lymphoma in the dose escalation phase; 9 patients were enrolled, including 3 at lowest dose and 6 that were treated at the MTD of 400 mg BID. It is still planned for 6 patients with advanced solid tumors and lymphoma with mutations in selected DNA repair genes to be enrolled into the expansion cohort to receive the maximum tolerated dose of veliparib in combination with nivolumab. However, due to funding issues, the study will perform an early analysis of preliminary efficacy after the next 6 patients are enrolled in the expansion cohort, all with the genetic mutation. According to the modified plan for the current trial, the study will be closed after the 6 additional patients will have been recruited.

Approximately 5 potentially eligible patients will be seen per month, and it is anticipated that at least 2 per month will be accrued. Patients will be recruited by all participating investigators in respective clinics within the Northwestern University Cancer Center network. Potential patients may be referred to the Principal Investigator (PI) at Northwestern University, [name] [name] at [contact].

Eligibility will be evaluated by the study team according to the following criteria. Eligibility waivers are not permitted. Subjects must meet all of the inclusion and none of the exclusion criteria to be registered to the study. Study treatment may not begin until a subject is registered. Please refer to Section 11 for complete instructions regarding registration procedures.

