5.0 STUDY PROCEDURES

Table 5: Study timeline

	Screening ^{a,b,c}	Induction (7 days) ^c	Cycle 1 (Cycle=28 days)			Cycle 2-4		Cycle 5 +	End of Treatment ^o	Follow Up ^p
		D1	D1	D8	D15	D1	D15	D1		
Study window				±1 day	±1 day	±3 days	±3 days	±3 days	±7 days	q3months
Informed Consent	X									
Medical History	X		X	X		X		X	X	
Physical Exam	X	X	X	X	X	X	X	X	X	
Vitals signs ^{d,i}	X	X	X	X	X	X	X	X	X	
ECOG PS	X	X	X	X			X	X	X	
AE reporting ^q		X	X	X	X	X	X	X	X ^q	X ^q
Concomitant Medications		X	X	X	X	X	X			X
CMP ^e	X	X	X	X	X	X	X	X	X	
CBC with differential ^f	X	X	X	X	X	X	X	X	X	
Pregnancy test ^g	X ^g		X							
Thyroid function test ^h	X									
PT/INR	X ⁱ									
Imaging (CT or MRI) ^j	X					X ⁱ		X ^j	X	
Tumor biopsy ^k	X									
Mutation testing	X ^r									
Blood for Tumor Markers ^l		X	X			X ^l			X	
Nivolumab infusion ^m			X		X	X	X	X ^m		
Veliparib ⁿ		X	X			X		X		
Survival										X

- Informed consent must be signed ≤ 30 days before registration. If signature is outside that window the patient must sign a new consent.
- Pre-study H&P and all labs must be ≤ 14 days before registration. Tumor measurements and radiologic evaluations must be ≤28 days before registration.
- The maximum time interval between registration and the first dose of study drug will be 14 days.
- Vital signs include pulse and blood pressure. Weight will be recorded at baseline. Height will be recorded at baseline only.
- Serum Chemistry will include calcium, chloride, magnesium, phosphorus, creatinine, sodium, potassium, blood urea nitrogen, bicarbonate, glucose, total bilirubin, aspartate aminotransferase (AST), alanine aminotransferase (ALT), alkaline phosphatase, albumin, and total protein.

- f. CBC: Performed pre-dose at each treatment visit (Day 1 & 15 of Cycles 1-4, and Day 1 of Cycle 5+). For patients experiencing significant drop in WBCs or platelets felt related to treatment, CBCs should be obtained more frequently (weekly or more frequently) to assess timing for retreatment or need for transfusion support.
- g. Serum or urine test only for women of childbearing potential; must be tested within 7 days prior to registration as well as C1D1 (within 24 hours prior to nivolumab treatment).
- h. Thyroid function tests will include thyroid stimulating hormone (TSH) with reflexfree T4. This will be done at baseline then only as clinically indicated thereafter.
- i. PT/INR is required at baseline (≤ 28 days prior to registration) for patients on anticoagulants.

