APPENDIX A- CONTRACEPTION REQUIREMENTS

Investigators shall counsel FOCBP and male subjects who are sexually active with FOCBP on the importance of pregnancy prevention and the implications of an unexpected pregnancy. Investigators shall advise FOCBP and male subjects who are sexually active with FOCBP on the use of highly effective methods of contraception from the time of treatment initiation to 5 months (for FOCBP) or 7 months (for males with FOCBP partners) after the last dose of nivolumab. Highly effective methods of contraception have a failure rate of < 1% per year when used consistently and correctly.

At a minimum, subjects must agree to the use of two methods of contraception, with one method being highly effective and the other method being either highly effective or less effective as listed below:

HIGHLY EFFECTIVE METHODS OF CONTRACEPTION

- a) Male condoms with spermicide
- b) Hormonal methods of contraception including combined oral contraceptive pills, vaginal ring, injectables, implants, and intrauterine devices (IUDs) such as Mirena® by FOCBP subject or male subject's FOCBP partner. Female partners of male subjects participating in the study may use hormone based contraceptives as one of the acceptable methods of contraception since they will not be receiving study drug.
- c) Nonhormonal IUDs, such as ParaGard®
- d) Tubal ligation
- e) Vasectomy.
- f) Complete Abstinence*

*Complete abstinence is defined as complete avoidance of heterosexual intercourse and is an acceptable form of contraception for all study drugs. Subjects who choose complete abstinence are not required to use a second method of contraception, but female subjects must continue to have pregnancy tests. Acceptable alternate methods of highly effective contraception must be discussed in the event that the subject chooses to forego complete abstinence.

LESS EFFECTIVE METHODS OF CONTRACEPTION

- a) Diaphragm with spermicide
- b) Cervical cap with spermicide
- c) Vaginal sponge
- d) Male Condom without spermicide*
- e) Progestin only pills by FOCBP subject or male subject's FOCBP partner
- f) Female Condom*

*A male and female condom must not be used together

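### The menses condition in the 3.1.10 definition of child-bearing potential also exempts women whose periods stopped because of cancer therapy or hormonal contraception

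*Combined protocol and SAP*

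**What the plan says.** Section 3.1.10 makes agreement to contraception an inclusion criterion for FOCBP and for men sexually active with FOCBP. Its note defines FOCBP as any woman who meets two listed criteria. Tubal ligation and chosen celibacy do not take a woman out of the definition. The first criterion is that she has had neither a hysterectomy nor a bilateral oophorectomy. The second is "Has had menses at any time in the preceding 12 consecutive months (and therefore has not been naturally postmenopausal for > 12 months".

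These provisions use the term or something close to it:

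- 3.1.11: "FOCBP must have a negative pregnancy test", to be done no more than 7 days before registration.
- Table 5 (Section 5.0), footnote g: "Serum or urine test only for women of childbearing potential; must be tested within 7 days prior to registration as well as C1D1". It neither uses the abbreviation FOCBP nor cites 3.1.10.
- Appendix A: "Investigators shall advise FOCBP and male subjects who are sexually active with FOCBP on the use of highly effective methods of contraception". For FOCBP the period runs from the start of treatment to 5 months after the last nivolumab dose. The appendix continues: "At a minimum, subjects must agree to the use of two methods of contraception". One of the two must be highly effective. Combined pills and several other hormonal methods are listed as highly effective; progestin-only pills are listed as less effective.

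The population is pretreated. Section 3.1.2 states: "All patients must have received, and be relapsed/refractory to at least one line of systemic therapy".

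**The concern.** The bracket in the second bullet opens with a word of inference. It states what follows from having had menses and sets no separate test. The inference runs one way only: menses in the past year rules out established natural menopause, but a year without menses does not establish it. Cancer therapy and hormonal contraception can also stop menses.

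Every patient has had systemic therapy and women are eligible from age 18, so therapy-induced amenorrhoea is plausible here. At stake is fetal exposure to the study drugs; Table 4.5 itself lists embryo-fetal toxicity for veliparib. A woman wrongly placed outside the definition has no contraception requirement, and a negative test is no longer a condition of her entry.

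**Working it through.** The plan gives no figure to reproduce. The check is to treat the definition as a logical rule and follow it through the provisions that depend on it.

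**Rule as worded.** FOCBP = (no hysterectomy and no bilateral oophorectomy) AND (menses at some time in the last 12 months). Nothing between the bullets makes them alternatives.

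**Cases, all with uterus and ovaries present:**

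| Case | Bullet 1 | Bullet 2 | FOCBP? | In line with the bracket? |
|---|---|---|---|---|
| (a) Menses in the last 12 months | met | met | yes | yes |
| (b) Natural menopause, more than 12 months | met | not met | no | yes |
| (c) No menses for 12 months after cancer therapy | met | not met | no | no |
| (d) No menses for 12 months on hormonal contraception | met | not met | no | no |

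A woman whose periods stopped less than 12 months ago falls under (a) and stays covered. Cases (c) and (d) are treated like (b), although neither is natural menopause.

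**What falls away in (c) and (d):**

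1. The 3.1.11 test as an eligibility condition. It applies to FOCBP only.
2. The contraception duty. Section 3.1.10 and the opening paragraph of Appendix A are addressed to FOCBP and to men with FOCBP partners. The two-method sentence speaks of subjects in general, but it follows that paragraph and takes its scope from it. The requirement therefore drops from two methods (or complete abstinence alone), during treatment and for 5 months after the last nivolumab dose, to none.
3. In case (d) the woman is using a method, but nothing obliges her to keep it or to add a second. If it is a progestin-only pill, Appendix A would not accept it as the highly effective one of the pair.

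**Tests per woman.** A FOCBP has 1 test within 7 days before registration (one sample serves both 3.1.11 and footnote g) and 1 at C1D1, so 1 + 1 = 2. For (c) and (d):

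- Reading A, footnote g in its ordinary meaning: a potentially fertile woman is covered, 2 tests remain, loss 2 − 2 = 0.
- Reading B, footnote g carrying the 3.1.10 definition: 0 tests remain, loss 2 − 0 = 2.

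The contraception gap is the same under both readings.

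**Other safeguards.** Section 3.2.17 excludes pregnant patients, 4.4 asks a patient who suspects pregnancy to tell her physician, 7.2.6 requires reporting and stops dosing once a pregnancy is known, and 11.3 requires a physician-signed eligibility checklist. None of these names a test or imposes contraception.

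**The case against.** The strongest reply is that the intent is visible. The bracket speaks of natural menopause, a physician signs the checklist, and nothing stops that physician from testing or counselling a younger woman without periods. This is loose drafting, and a careful investigator would probably act sensibly. That stands as a reason to rate the point low. It does not remove the point, because the wording requires nothing for such a woman.

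A reader might infer that she would certainly go untested. The documents do not support this: footnote g does not use the defined term, and on its ordinary meaning both tests still apply. A reader might also infer that the plan lets a pregnant woman enrol. It does not; 3.2.17 bars her and Section 3.0 allows no eligibility waivers. The gap concerns detection and prevention.

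The clinical premise lies outside the documents. No passage says that 12 months of treatment-related amenorrhoea can coexist with fertility, or how often. The affected patient must also be of fertile age, still fertile, at risk of conception and among the few patients left to enrol. This objection stands, and no frequency is claimed here.

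Nor do the documents show how many of the six places were still open at this version. Section 3.0 says "it is anticipated that at least 2 per month will be accrued", but that planned rate is no record of enrolment and cannot show that accrual had finished.

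**Conclusion.** The point holds as a minor wording defect. Bullet 2 of 3.1.10 exempts amenorrhoea of 12 months from any cause, while its own bracket shows that only natural menopause was meant. For a woman whose amenorrhoea comes from cancer therapy or hormonal contraception, the contraception duty and the 3.1.11 eligibility test fall away. The loss of scheduled tests is conditional: 0 of 2 under reading A of footnote g, 2 of 2 under reading B.

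The conclusion about the wording rests on the text alone. Its clinical relevance rests on the assumption that such amenorrhoea can coexist with fertility. The number of women affected cannot be derived from the documents and is probably very small, with at most 6 patients left to enrol under the plan. Neither the MTD nor the ORR analysis is touched.

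**What to change.** Two edits in the next amendment:

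- Section 3.1.10, bullet 2, reworded as: *Has not been naturally postmenopausal for > 12 consecutive months; amenorrhoea caused by cancer therapy or hormonal contraception does not by itself exclude childbearing potential.*
- Table 5, footnote g: replace *women of childbearing potential* with *FOCBP as defined in 3.1.10*.

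The edits belong together, so that footnote g has one meaning and the tests follow the corrected definition. No age limit is needed.

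The cost is one sentence and one term. Extra tests per affected woman are 0 if footnote g is already read in its ordinary meaning and 2 if it is not, of a kind already scheduled. The downside is that a few women who are in fact infertile would be tested and asked to use contraception. Because 3.1.10 and Appendix A also apply the FOCBP definition to the partners of male patients, the contraception duty of a few men would widen as well, for treatment plus 7 months.

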3.2 Exclusion Criteria

3.2.1 Patients who have had radiotherapy ≤ 14 days prior to registration are not eligible.

3.2.2 Patients who have received systemic chemotherapy or investigational agents ≤ 28 days prior to registration are not eligible.

3.2.3 Patients are not eligible who have had major surgery ≤ 14 days prior to registration. Please contact PI and QAM for questions about specific surgical procedures.

3.2.4 Patients are not eligible who have received prior PARP inhibitors (including but not limited to veliparib, talazoparib, rucaparib, and olaparib).

3.2.5 Patients are not eligible who have received prior immunotherapy including interleukin-2 and immune checkpoint antagonists and/or agonists (including but not limited to PD-1, PD-L1, CD137, or OX40).

NOTE: Single agent anti-CTLA4 monoclonal antibody treatments are permitted. Cancer vaccine therapies are permitted.

3.2.6 Patients with the following histologies are not eligible for either study cohort given known response to PD-1/PD-L1 inhibitor monotherapy:
Non-small cell lung cancer, squamous cell carcinoma of head and neck, melanoma, renal cell carcinoma, bladder cancer, Hodgkin's lymphoma, Merkel cell carcinoma, and MSI-H colorectal cancer

3.2.7 Patients with deleterious BRCA 1/2 mutated ovarian cancer are not eligible.

3.2.8 Patients are not eligible who have had a prior allogeneic stem cell transplant.
NOTE: Autologous stem cell transplant is acceptable.

3.2.9 Patients who are taking any herbal (alternative) medicines are NOT eligible for participation. Patients must be off any such medications by the time of registration for ≥ 14 days.
NOTE: Vitamin supplements are acceptable.

3.2.10 Patients requiring systemic treatment with corticosteroids (>10 mg daily prednisone equivalents) or other immunosuppressive medications ≤ 14 days prior to first dose of study drug are not eligible.
NOTE: Inhaled and intranasal corticosteroids are permitted. A brief (less than 3 weeks) course of corticosteroids for prophylaxis (eg, contrast dye allergy) or for treatment of non-autoimmune conditions (eg, delayed-type

hypersensitivity reaction caused by a contact allergen) is permitted.

- 3.2.11 Patients who receive a live attenuated vaccine ≤ 28 days prior to registration are not eligible.
- 3.2.12 Patients must have no history of CNS metastasis at the screening assessment.
NOTE: *Patients with stable brain mets which have been treated are eligible. Patients with suspected symptoms of CNS metastasis should undergo CNS imaging at the time of screening to rule out active metastasis.*
- 3.2.13 Patients who have had a prior severe infusion reaction to a monoclonal antibody are not eligible.
- 3.2.14 Patients are not eligible who have a history of or active autoimmune disease within the past 3 years with the following exceptions:
- Vitiligo or alopecia
 - Hypothyroidism on stable doses of thyroid replacement therapy
 - Psoriasis not requiring systemic therapy within the past 3 years
- 3.2.15 Patients with a history of primary immunodeficiency disease or tuberculosis are not eligible.
- 3.2.16 Patients who have an uncontrolled current illness including, but not limited to any of the following, are not eligible:
- Uncontrolled pulmonary, renal, or hepatic dysfunction
 - Ongoing or active infection requiring systemic treatment including hepatitis B and hepatitis C
 - Known active or chronic viral hepatitis or human immunodeficiency virus (HIV)
 - Psychiatric illness/social situations that would limit compliance with study requirements
 - Clinically significant gastrointestinal disease or digestive dysfunction compromising absorption of veliparib
 - Any other illness or condition that the treating investigator feels would interfere with study compliance or would compromise the patient's safety or study endpoints
- 3.2.17 Female patients who are pregnant or nursing are not eligible.
- 3.2.18 Patients with a prior diagnosis of cancer must not have received treatment in the last 3 years prior to registration.
NOTE: treatments used as a recurrence prevent are eligible.
NOTE: *Patients with a history of completely resected non-melanomatous skin carcinoma or successfully treated in situ carcinoma are eligible.*
- 3.2.19 Patients must not have a history of prior stroke, transient ischemic attack (TIA), pulmonary embolism, or untreated deep vein thrombosis.
NOTE: *Patients may be eligible if they have received at least 3 months of anticoagulation for a deep vein thrombosis.*

